7.2.2. Male Participants

Male participants must use a male condom (with or without spermicide) if sexually active with a female of childbearing potential from the start of the screening period until 12 weeks after the last administration of study drug. Male participants should be encouraged to inform their female sexual partners that they are participating in a Phase 2 clinical study.

Male participants who have documented vasectomy with medical confirmation of success are not required to use contraception.

8. INVESTIGATIONAL PRODUCT(S)

8.1. Dosage and Administration

SLN360 is provided as a solution for injection for subcutaneous use in glass vials. A vial (2R vial) contains 0.5 mL (extractable volume) of an aqueous sterile solution of SLN360 drug substance with a concentration of 200 mg/mL (as free acid form). The vials are intended for single use. SLN360 will be supplied by the Sponsor or designee, along with the batch/lot numbers and Certificates of Analysis.

Each dose of SLN360 or placebo will be administered via subcutaneous injection by appropriately qualified clinical study site staff. The injection will be delivered in the abdomen, avoiding areas where the skin is red, bruised, tender, indurated or in sites of previous scars. Where other medicinal products are required to be given by subcutaneous administration, these should be administered preferably at different sites.

Study Number: SLN360-002	Compound No.: SLN360
Protocol	Version: 1.0

Individual injection volume at each injection site will not exceed 1.5 mL, and up to two injection sites may be used to achieve the required dose. Please refer to the IMP Handling Manual for further guidance.

Where multiple injections are required in one dosing session, injection sites ideally should be separated by a few centimetres, according to local practice. When multiple injections are given, injection sites should be rotated to a different location (i.e., not administered in precisely the same place for subsequent administrations) and a new quadrant of the abdomen should be used for each injection. It is recommended to proceed around the quadrants in a clockwise direction. Injection sites should be recorded in the eCRF.

Participants will be dosed at the timepoints outlined in the Time and Events tables ([Appendix 15.1](#) and [Appendix 15.2](#)).

8.2. Dose Rationale

Data from SAD administration in the FIH study and from modelling of nonclinical data (LYO-X Report No.: [LYO-X-2022-06-0003](#)) indicate that the safe, tolerable and effective doses of SLN360 for evaluation in this Phase 2 study are 300 mg and 450 mg. SLN360 and placebo will be administered via subcutaneous injection in multiple doses. Placebo and three SLN360 dosing regimens will be evaluated: 300 mg Q16W, 300 mg Q24W and 450 mg Q24W.

Efficacy is defined as a combination of magnitude of Lp(a) reduction and the duration over which that reduction persists. Data from the FIH study suggest that a reduction of 80 to 90% in Lp(a) levels from baseline sustained for more than 12 weeks is anticipated at these doses.

8.2.1. Pharmacokinetic-pharmacodynamic Modelling for Dose Selection

Recommended Dose Range:

Safety data from the completed SAD part of the ongoing Phase 1 study support the dose range in this Phase 2 study of 300 to 450 mg based on the summarised data in [Section 1.1.3](#). The 300 mg dose in the SAD part of the Phase 1 study was well tolerated with no concerning treatment-associated safety signals. The maximal dose, 600 mg, was associated with ISRs (up to CTCAE grade 2), all of which resolved. Plasma PK for these doses was broadly dose proportional. From an efficacy perspective, lowering of Lp(a) concentration from baseline by at least approximately 80% is the objective of the SLN360 programme; this magnitude of effect or greater was observed after single doses of 100 mg, 300 mg and 600 mg in the SAD part of the Phase 1 study. Exaggerated pharmacology is not a concern with Lp(a)-lowering as individuals have been identified with near-zero circulating concentrations of Lp(a) and with no reported adverse

Study Number: SLN360-002	Compound No.: SLN360
Protocol	Version: 1.0

consequences. Therefore, the benefit: risk balance based on the available clinical and nonclinical data supports a starting dose of 300 mg in this study.

Maximum Supported Dose:

Data from the SAD part of the Phase 1 study, suggest lower tolerability of the maximum evaluated dose of 600 mg. In brief, ISRs accompanied by transient leukocytosis and rises in C-reactive protein were observed at the 600 mg dose. Considering these findings, we do not intend to pursue the 600 mg dose further in development. However, the SAD Phase 1 data and PK-PD modelling appear to support a favourable benefit: risk when evaluating doses up to 450 mg based on predicted magnitude and duration of Lp(a) lowering for clinical benefit in patients with ASCVD.

Pharmacokinetic-pharmacodynamic Modelling:

The data from the SAD part of the Phase 1 study was used to construct a population PK-PD-based SLN360 model. The model structure was based on modelling of preclinical studies in non-human primates and included a liver compartment and associated liver parameters. A small subset of parameters in the human model were fixed to values allometrically scaled from the non-human primate model, a choice justified by the lack of liver data in humans and the ability of the full non-human primate model predict the Phase 1 data after scaling to human. All model parameters not fixed to values allometrically scaled from non-human primates were estimated using the Phase 1 study PK and PD data.

Data used for the modelling included:

- Non-human primate plasma and liver SLN360 concentrations, serum Lp(a) concentrations
- Human plasma SLN360 and Lp(a) concentration from SAD part of the Phase 1 study for single doses of placebo and 30, 100, 300 and 600 mg of SLN360

Full details of the nonclinical studies are available in the IB. Modelling tested a range of covariates: age, body weight, sex, eGFR (PK estimates only), and baseline Lp(a) (PD estimates only). No covariates were included in the final model used for predictions of PK and PD in this Phase 2 study.

Simulations were prepared for a range of repeat dosing regimens, including but not limited to:

[figure not shown]
- Three hundred mg dosing every 3, 4 and 6 months (Q3M, Q4M and Q6M, respectively)
- Four hundred and fifty mg Q3M, Q4M and Q6M

Study Number: SLN360-002	Compound No.: SLN360
Protocol	Version: 1.0

Each simulation included 300 individuals, from which were derived the simulated liver concentrations of SLN360, longitudinal profile of Lp(a) change over 24 months and the time-averaged change in Lp(a) over a dosing interval after the final simulated dose.

The simulated SLN360 liver exposure is shown in [Figure 3](#). With repeated dosing, only modest increments in liver exposure are predicted, with the increment diminishing after the second dose.

Figure 3 Predicted liver SLN360 concentrations after repeat dosing with a range of doses and regimens

[figure not shown]

Note: simulated median (red line), 5th and 95th prediction interval (red area) from 300 simulated individual profiles.

The profiles for the dosing regimens proposed for the planned Phase 2 study are in [Figure 4](#).

Study Number: SLN360-002	Compound No.: SLN360
Protocol	Version: 1.0

Figure 4 Simulated serum Lp(a) levels for the dosing regimens planned in the proposed Phase 2 study

[figure not shown]
Note: simulated median serum Lp(a) (red line), 5th and 95th prediction interval (red area) from 300 simulated individual profiles. Baseline (dashed line). Target % lowering from baseline = 20% (dotted line).

The most clinically meaningful measure of SLN360 efficacy is a function of the magnitude and duration of Lp(a) lowering. This can be quantified by the time-averaged change in Lp(a) after dosing. [Figure 5](#) illustrates the simulated time-averaged change in Lp(a), from 300 simulated individuals. The time period for the average is the change from the last dose administered in each regimen to 12 months. For Q4M regimens this is the period after the third dose and for Q6M regimens it is the period after the second dose. In both cases, the time periods represent a single dosing interval.

[figure not shown]
Study Number: SLN360-002 Protocol	Compound No.: SLN360 Version: 1.0
--------------------------------------	--------------------------------------

Figure 5 Simulated time-averaged change in serum Lp(a) for a range of dosing regimens, including those planned for the proposed Phase 2 study

A

B

Lp(a)=lipoprotein(a); q4m=dosing every 4 months; q6m=dosing every 6 months

A) Serum Lp(a) predicted time-average % change from baseline for dosing interval (after final simulated dose).

B) Illustration of sources of data for time-averaged change in Lp(a). Based on 300 simulated individual profiles. Trough refers to trough exposure for a continuous Q6M dosing interval.

The percentage of the simulated population with time-averaged reduction in Lp(a) >80% lower than baseline values are described in [Table 7](#). The doses planned in the proposed Phase 2 study are highlighted.

Study Number: SLN360-002	Compound No.: SLN360
Protocol	Version: 1.0

Table 7 Percentage of population with time-averaged reduction Lp(a) >80% lower than baseline

Regimen	SLN360 Doses				
	100 mg	150 mg	200 mg	300 mg	450 mg
4 x Q3M	68.7%	85.3%	93.3%	98.7%	99.7%
3 x Q4M	40.7%	69.7%	82.7%	94.0%	97.3%
2 x Q6M	12.3%	29.7%	43.7%	68.7%	86.7%

Q3M=dosing every 3 months; Q4M=dosing every 4 months; Q6M=dosing every 6 months

Cells highlighted in grey indicate the doses to be evaluated in this study.

Based on all of the PK-PD modelling findings, the following conclusions were made:

- Liver exposure reaches near the steady-state after the second dose of SLN360 and substantial liver accumulation is not anticipated with repeat dosing
- Efficacy of SLN360, with respect to Lp(a)-lowering, is meaningfully characterised as a time-averaged change in serum Lp(a) from baseline
- Dosing regimens of 300 mg Q4M, 300 mg Q6M and 450 mg Q6M allow exploration of a dose range that offers the combination of anticipated safety, frequency of administration and time-averaged reduction in Lp(a) that best support a favourable benefit: risk in the target population

8.3. Maintaining the Blind

Participants, Investigators and specific academic personnel and the CRO along with Sponsor staff will be blinded to treatment group allocation. The nature of the treatment supply means that the Pharmacist will be unblinded with appropriate oversight; details will be provided in the Study Blinding Plan.

8.3.1. Emergency Unblinding

Emergency unblinding is defined as a purposeful action to reveal the actual treatment assignment of the study participant whereby the knowledge of the treatment assignment is essential for the clinical management, safety and/or welfare of a specific participant. The Investigator should discuss with the Medical Monitor before unblinding, if possible. The Sponsor must be notified within 24 hours after breaking the blind.

The IRT system that is used for participant randomisation also allows unblinding at any time should it be required. The roles of who can unblind are defined in the system and include the Principal Investigator at the site. Should the online tool not be available, a helpdesk with 24 hours/day, 7 days/week, 365 days/year availability is also available for unblinding via telephone (please see IRT Reference Guide).

Study Number: SLN360-002	Compound No.: SLN360
Protocol	Version: 1.0

An email notification will be sent out immediately after the unblinding has occurred to the roles defined in the IRT requirements, including the Principal Investigator at the site, the Sponsor, the Safety Manager and the Medical Monitor. The notification of unblinding will be filed in the Investigator Site File and includes the following information:

- Participant number
- Site number
- Study/protocol number
- Date and time of unblinding
- Reason for unblinding

The notification of unblinding will not contain the actual treatment assignment.

8.4. Treatment Assignment

This is a randomised controlled study; participants will be assigned their treatment using IRT. Participants will be allocated to a treatment group in accordance with the randomisation schedule. The randomisation schedule will be computer generated.

Randomisation (allocation to treatment) will occur just before the participant receives their first dose of study drug. Once assigned, randomisation numbers shall not be reassigned. Randomisation numbers will be assigned and maintained using IRT. Each participant will be allocated a unique participant identifier at screening that will be used throughout the study.

Participants will be randomised in a 1:1:2:2:2 ratio to the groups described in [Section 4.1.1](#) to receive either SLN360 or placebo.

Further details on the randomisation process will be provided in the IMP Handling Manual.

8.5. Packaging and Labelling

Study treatment will be supplied in single-use, pre-filled glass vials that will have been labelled and packaged before distribution to the study sites. Study treatment will be labelled and packaged under the responsibility of the Sponsor. No medication can be re-labelled or repackaged without prior approval from the Sponsor.

Medication will be provided to the sites in an open-label format. The labels will contain all information required to meet the applicable local regulatory requirements. The syringe labels applied following dispensing will be blinded.

Further information on the study drug packaging, labelling and dispensing will be provided in the IMP Handling Manual.

Study Number: SLN360-002	Compound No.: SLN360
Protocol	Version: 1.0

8.6. Preparation

Details on the preparation of SLN360 will be provided in the IMP Handling Manual.

8.7. Handling and Storage

SLN360 must be kept in an appropriate, secure, locked area and stored in accordance with the conditions specified on the labels. SLN360 will be stored between 2°C (35.6°F) and 8°C (46.4°F).

Placebo treatment (commercial NaCl injection, 0.9% weight/volume administered via subcutaneous injection) will be supplied by the Sponsor (or designee). Placebo will be stored in accordance with the conditions specified on the label. All study drug vials/ampoules are single-use and any unused portion remaining in the vial must be discarded.

8.8. Product Accountability and Assessment of Compliance

The appropriate study personnel will maintain a log of all study drugs received, dispensed, destroyed and returned. Drug supplies will be inventoried and accounted for throughout the study. Local site drug destruction is acceptable, provided it is authorised by the Sponsor and a certificate of destruction is made available.

The Investigator's unblinded designee will ensure that each participant receives the appropriate dose of the study drug. Only participants enrolled in the study may receive study treatment and only site staff, as outlined in the site accountability log, may administer study treatment.

8.9. Treatment of Investigational Product Overdose

From a primary pharmacological perspective, participants are individuals who have elevated Lp(a) levels and are at high risk of a first ASCVD event. The majority of the general population has low (less than approximately 50 mg/dL) circulating Lp(a) levels [Kamstrup *et al*, 2009]. These low levels are not associated with adverse health outcomes; for instance, individuals with no detectable Lp(a) have been identified, and they display no substantial detrimental effects [Lim *et al*, 2014; Emdin *et al*, 2016]. Therefore, potential harmful effects of reduced Lp(a) levels are not expected to be a primary concern, and exaggerated primary pharmacology is not expected to occur. Since SLN360 is administered in a controlled clinical setting by healthcare professionals the potential for overdose is extremely low. The Sponsor will collect information pertinent to overdose across the clinical development program. Further information regarding overdose will be provided by the Sponsor to Investigators in the IB.

Study Number: SLN360-002	Compound No.: SLN360
Protocol	Version: 1.0

8.10. Occupational Safety

No specific risks have been identified for staff handling the study treatment. The Material Safety Data Sheets will be made available where required by local regulations.

9. CONCOMITANT MEDICATIONS AND NON-DRUG THERAPIES

9.1. Recording Prior and Concomitant Medication

All concomitant medications, including medication given in the 30 days before study treatment administration and during the study, must be recorded in the eCRF along with the indication for which it was used. The generic name of the drug should be specified along with the dose, frequency, duration and route of administration of treatment.

Any diagnostic, therapeutic or surgical procedure performed during the study period should be recorded in the eCRF, including the dates, indication, description of the procedure(s) and any clinical findings, if applicable.

9.2. Permitted Medications

Other than the therapies listed in [Section 9.3](#), the use of any concomitant medication/therapy, including over-the-counter medications that is deemed necessary for treating the participant is permitted during the study. Any medication used for the management of dyslipidaemia (including statins, ezetimibe, bempedoic acid, fibrates, omega-3 fatty acids, coleselvam and implitapide) must have been at a stable, maximum tolerated dose for at least 8 weeks prior to screening and expected to remain stable for the duration of the study (in the opinion of the Principal Investigator). Sex hormone replacement therapy for male or female participants will only be permitted if the therapy has been prescribed at a stable dose for at least 8 weeks prior to screening and is expected to remain stable for the duration of the study (in the opinion of the Principal Investigator).

Acetaminophen (paracetamol), up to a maximum dose of 2 g/day, will be permitted for use as an antipyretic and/or analgesic. Aspirin (up to a maximum dose of 325 mg/day) will be permitted for use as an antipyretic and/or analgesic, and for primary or secondary prevention of CVD. Oral contraceptives are permitted.

9.3. Prohibited Medications and Procedures

The following concomitant treatments are not permitted during the study:

- Initiation of medication or therapies significantly affecting Lp(a) levels (including but not restricted to PCSK9 inhibitors, prescription dose niacin, fibrates and anti-oestrogen therapy)

Study Number: SLN360-002	Compound No.: SLN360
Protocol	Version: 1.0

- Initiation of statins and/or ezetimibe
- Initiation of lipid or lipoprotein apheresis
- Initiation of oligonucleotide therapy, including antisense oligonucleotides, and siRNA, other than SLN360. Vaccines using mRNA technology are permitted
- Initiation of sex hormone replacement therapy for male or female participants
- Initiation of anti-oestrogen or oestrogen receptor modulator (e.g., tamoxifen)

If during the course of the study, a participant needs additional medication, surgery or an investigation that affects participation in the study or otherwise compromises either the participant's safety or the integrity of the data collected, this should be discussed with the Medical Monitor. The participant may be withdrawn from the study, if deemed necessary, and replaced if appropriate; all participants that have been dosed should complete follow-up assessments even if withdrawn. The participant's treating physician(s) must be informed of the experimental therapy and the likely effects of SLN360 on Lp(a) levels, other plasma lipid fractions and markers of toxicity.

10. PARTICIPANT COMPLETION AND WITHDRAWAL

10.1. Participant Completion

The participant will be classed as having completed the study once they have completed the EoS visit, which will be up to 36 weeks after the last administration of treatment, depending on group, or an early withdrawal visit.

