4.2. Study and Participant Termination

Changes in the health status of the participant since the screening visit, including laboratory results, will be checked prior to administration of the study treatment. Participation of a participant in this clinical study will be discontinued for any of the following reasons:

- Withdrawal of consent
- Termination of the study by the Sponsor or a regulatory authority

Participants are free to withdraw consent from the study (which means permanent discontinuation of study drug administration and all follow-up assessments) at any time without prejudice. Note that discontinuation of study drug in and of itself is not considered withdrawal of consent.

The Investigator must temporally interrupt or permanently discontinue study treatment for the participant if administration is believed to be contrary to the best interests of the participant; further details are provided in [Section 10.2.3](#).

Study Number: SLN360-002	Compound No.: SLN360
Protocol	Version: 1.0

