10.2.2. Participant Withdrawal from Study

Participants may withdraw from the study at any time and for any reason without the need for justification. Participants may also be withdrawn by the Investigator if, in the Investigator's opinion, further participation in the study would be deleterious to the participant's health. Reasons for withdrawal could include unacceptable adverse reactions, protocol violation or administrative reasons. To maintain the value and integrity of the study, excessive withdrawals should be avoided where possible.

Where consent remains, every effort must be made to follow-up participants and, other than re-dosing, the scheduled trial assessments should be performed if possible. A reason for withdrawal and an early withdrawal clinic assessments (consisting of assessments included in the Week 36 and EoS visit) as per the Time and Events tables ([Appendix 15.1](#) and [Appendix 15.2](#)) are essential.

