3.3 Subject Data and Study Conduct

3.3.1 Subject Disposition

Counts and percentages of subjects who were screened (signed informed consent), discontinued early during screening (screen failures), and randomized will be summarized in total based on all screened subjects. Reasons for early discontinuation will also be summarized.

Counts and percentages of subjects who were randomized, discontinued treatment early, completed study treatment, discontinued early from the study, and completed the study will be summarized by treatment and in total based on all randomized subjects. Primary reasons for early discontinuation treatment and study will also be summarized. Early discontinuation treatment and study due to Coronavirus disease 2019 (COVID-19) will be summarized.

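### Does Protocol 10.1 cause participants who withdraw early to be counted as having completed the study?

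*Protocol*

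**What the plan says.** Protocol 10.1 contains the only definition of study completion in the two documents: "The participant will be classed as having completed the study once they have completed the EoS visit", and the sentence continues "which will be up to 36 weeks after the last administration of treatment, depending on group, or an early withdrawal visit".

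Protocol 10.2.2 deals with withdrawal from the study. It describes the early withdrawal assessments as essential. Where consent remains, it adds that "other than re-dosing, the scheduled trial assessments should be performed if possible". Protocol 9.3, on participants who need a prohibited treatment, says that "all participants that have been dosed should complete follow-up assessments even if withdrawn". Protocol 4.2 uses a narrower notion: withdrawing consent from the study is something "which means permanent discontinuation of study drug administration and all follow-up assessments".

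SAP 3.3.1 plans the disposition table. Subjects who "discontinued early from the study, and completed the study will be summarized by treatment and in total based on all randomized subjects". It adds: "Primary reasons for early discontinuation treatment and study will also be summarized". It does not define either study-level status, does not refer to Protocol 10.1, and does not say that the two are exclusive. SAP section 6 reports no departures from the protocol's analyses, and SAP section 7 leaves detailed programming to a separate document.

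**The concern.** A disposition table should let the reader see how many participants reached the end of the study and how many left before it. If the protocol's definition is carried into the SAP table word for word, someone who leaves the study and attends a withdrawal visit satisfies the completion definition and is also an early discontinuation. The completed row would then be too high, and the two rows could add up to more than the number randomised.

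Retention would look better than it was, in a trial whose last assessment is at Week 60, well after the final dose. The distortion would also be larger, in percentage points, in the small placebo groups than in the SLN360 groups.

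**Working it through.** **1. The one figure in the sentence.** EoS is at Week 60 (Protocol 4.1.3). The last dose is at Week 24 in the Q24W groups and Week 32 in the Q16W groups (Protocol 4.1.1).

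- Q24W: 60 − 24 = 36 weeks
- Q16W: 60 − 32 = 28 weeks

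This reproduces the stated maximum of 36 weeks and its dependence on group. The timing is sound; only the closing phrase of the sentence is in question.

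**2. How the sentence can be read.** The withdrawal visit may be an alternative to the EoS visit or a form of it. Either way it counts as completion. A third reading is grammatical but strained: the withdrawal visit is a second starting point from which the time to EoS is measured. Under that reading there is no overlap. I take the natural reading.

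**3. Size if applied literally.** Let N be the number randomised, W the number who withdraw from the study, and V the number of those who attend an early withdrawal visit.

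- Completed, withdrawal visit not counted: N − W
- Completed, Protocol 10.1 taken literally: N − W + V
- Sum of the two rows, taken literally: N + V

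The overstatement is V. From the planned group sizes (Protocol 5.1), one such participant adds 1/160 = 0.625 points overall, 1/40 = 2.5 points in an SLN360 group and 1/20 = 5 points in a placebo group.

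The documents give neither W nor V. The table uses assumed values, with N = 160:

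| W (assumed) | Visit not counted | Literal, V = W/2 | Literal, V = W | Sum of rows (V = W/2; V = W) |
|---|---|---|---|---|
| 4 | 156 (97.5%) | 158 (98.75%) | 160 (100%) | 162; 164 |
| 8 | 152 (95%) | 156 (97.5%) | 160 (100%) | 164; 168 |
| 16 | 144 (90%) | 152 (95%) | 160 (100%) | 168; 176 |
| 24 | 136 (85%) | 148 (92.5%) | 160 (100%) | 172; 184 |

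The V = W column is an upper limit. It simply restates the assumed withdrawal rate, and it is not reached if anyone who withdraws consent has no further assessments (Protocol 4.2).

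**4. What the overlap would touch.**

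- *Discontinued row:* unchanged. W does not depend on how completion is defined. SAP 3.3.1 reports it with primary reasons, and Protocol 12.4.4.2.1 also calls for early withdrawals to be tabulated by treatment group with reasons.
- *Recovering the completed figure:* at the final analysis, N minus the discontinued row gives it directly.
- *Populations:* the Safety and Pharmacodynamic Populations (SAP 3.2) depend on dosing and evaluable data, not on completion.
- *Primary analysis:* SAP 3.4.1 uses a treatment policy strategy and scheduled Lp(a) values to Week 36. Its rule for participants whose data stop early depends on the date of the last available measurement, not on disposition status.
- *Sample size:* SAP 2.2.4 makes no use of completion.

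**The case for a change.** The best case for a change is that it costs almost nothing and that the SAP is where it belongs. Protocol section 12 assigns derivation algorithms and data-handling rules to the SAP, and SAP section 6 does nothing to displace Protocol 10.1. Subtraction also fails at the Week 36 database lock if disposition is tabulated then: participants still in follow-up are neither completed nor discontinued, while someone who withdrew earlier could already count as completed. That is correct as far as it goes. At that lock, however, a row for study completion says little in any case, and the discontinued row, which is the informative one, is still right.

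A second argument is that a withdrawn participant who keeps attending and reaches Week 60 also falls in both rows, without any withdrawal visit. This is weaker. Counting a person who attended the EoS visit as a completer applies the main part of Protocol 10.1. It is an overstatement only against a standard of reaching Week 60 without ever withdrawing, which neither document sets. The protocol is also loose here: section 4.2 equates withdrawing consent from the study with the end of all follow-up, while 9.3 and 10.2.2 ask for continued visits from people they call withdrawn. How to class them is a convention, and either choice is defensible.

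What stands is that the closing words of Protocol 10.1 are poorly chosen and that SAP 3.3.1 does not define its two study-level rows.

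**Conclusion.** The wording is loose, but no change to the plan is needed. Protocol 10.1 reads as though its last phrase was meant to say when participation ends; taken literally it says more than that. A statistician building the table in SAP 3.3.1, with primary reasons for discontinuation reported in the same summary, would ordinarily treat completed and discontinued as exclusive. If the eCRF or the programming specifications already do so, writing the definition down would alter no number.

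If the wording were nevertheless applied literally, one descriptive row would be too high by the number of withdrawn participants with a withdrawal visit, at 0.625 points each overall. With an assumed 16 withdrawals out of 160, that is between 0 and 10 points. These figures rest on the planned group sizes. Protocol 9.3 allows replacement of withdrawn participants, so the actual denominator may differ. Early discontinuations and their reasons would still be reported correctly, and no estimand, population, test, power figure or conclusion would move.
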